 - thrombotic events (microangiopathy including capillary leak syndrome), disseminated intravascular coagulation, deep vein thrombosis, pulmonary embolism, cerebral vein thrombosis, peripheral thrombosis, thrombosis with thrombocytopenia and ischemic strokes, acute coronary syndrome (acute myocardial infarction, unstable angina, and new onset angina),
 - bleeding events including haemorrhagic stroke (no subarachnoid),
 - composite endpoint: Venous thrombosis (including pulmonary embolism and deep vein thrombosis)
 - composite endpoint: Arterial thrombosis (including acute coronary syndrome and ischemic stroke),
 - composite endpoint: stroke (including haemorrhagic and non-hemorrhagic stroke)
 - heart failure, and stress cardiomyopathy.
- The incidence of immune/inflammatory events: encephalitis (including acute demyelinating encephalomyelopathy and meningoencephalitis), Guillain-Barré Syndrome, Bell's palsy, immune thrombocytopenia, thrombocytopenia, transverse myelitis and cardiac inflammatory disorders (including myocarditis and pericarditis) within 1-42 days.
- The incidence of sensorineural hearing loss within 1-60 days.
- The incidence of asthma exacerbation within 1-14 days.

Non-acute events (events expected to be recorded >60 days after vaccination)

- The incidence of new-onset autoimmune thyroiditis, multiple sclerosis, acute aseptic arthritis, and type 1 diabetes mellitus within 1-365 days.

Newly identified AESI may be incorporated into the list of AESI to be investigated by the current study if a safety signal occurs.

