8.1.2. Overview of Study Design for Safety Evaluation Study

Evaluation of safety concerns will be conducted using a retrospective observational study in electronic health care databases of various types in Europe. Eligible individuals will be included in the study from the start of Ad26.COV2.S vaccination in each participating country, and the study will end at the last date of data availability in each database.

For each AESI, the study design of the safety evaluation study will depend on whether the AESI is an acute or non-acute event and follow the decision framework described in the ACCESS template protocols for evaluation of safety events in electronic health care databases ([Dodd 2020](#)).

The primary study design for the evaluation of acute events (events expected to occur within 2, 14, 28, 42, or 60 days of vaccination) will be a self-controlled risk interval (SCRI) design with pre- and post-vaccination control window and for non-acute events (events expected to occur within 365 days) will be a cohort design with concurrent unexposed comparators. Additionally, the cohort analysis will also include two active comparator groups: one viral vector vaccine comparator group (i.e., Vaxzevria[®] [AZD1222] by Oxford/AstraZeneca) and one mRNA vaccine comparator group (i.e., Comirnaty[®] [tozinameran] by Pfizer/BioNTech and/or Spikevax[®] [elasomeran] by Moderna), where possible (pending on the feasibility analysis with a maximum follow-up time of one year).

In sensitivity analyses, an equivalent cohort design will also be used to assess acute events. When it is established that data sources do not capture vaccinations well during the feasibility assessment, we will conduct a sensitivity analysis excluding these data sources from the cohort analysis with non-exposed comparators for the non-acute events, to avoid misclassification of exposure.

Another sensitivity analysis will compare the Ad26.COV2.S vaccine with active comparators (1) a 1-dose strategy and (2) a 2-dose strategy.

Individuals start follow-up at the start of each risk window and end follow-up at the earliest occurrence of latest data availability of the databank, individual exit from the database, completion of the study period, or death. At least one year of enrolment prior to the index date (date of vaccination) will be required to determine whether individuals meet the study criteria and to define baseline characteristics. If more historical data is available, this will be included.

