8.1.2.1. Self-controlled Risk Interval Design (Primary Study Design for Acute Events)

The SCRI design will compare the risk of the AESI in a post-vaccination risk window to a pre-vaccination control window (sensitivity analysis) and post-vaccination control window (main analysis) within the same individual.

The SCRI design will include only individuals in the primary analysis who received at least one first-ever dose of the Ad26.COV2.S vaccine during the study period. Vaccinated individuals enter the study at the date of the start of the pre-vaccination control window. The SCRI design will compare the risk of each outcome during the post-vaccination risk window following the COVID-19 dose with a self-matched control interval that may be prior to vaccination, or after the vaccination risk window, to assess the baseline risk of the outcome. The control window will have the same maximum length as the risk window to minimise time-varying confounding that cannot be measured. In case the follow-up time does not capture the maximum post-vaccination risk or control window due to right censoring, all available follow-up time will be utilized. Follow-up will be censored upon vaccination with another COVID-19 vaccine or end of follow-up. A washout period between the control and risk window will be applied to minimise capturing of prevalent events during the risk window. A post-vaccination control window may induce a bias towards the null when an AESI that was identified during the vaccination risk window, is captured again during the control window due to a re-admission instead of reoccurrence of the AESI. This situation is more likely to be encountered for acute potentially recurring events such as cardiac events (including acute coronary syndrome, myocarditis, pericarditis, arrhythmia, and stress cardiomyopathy). Moreover, due to lag-times in updating the relevant databanks, there is a higher risk that the post-vaccination control window may not capture all events and underestimate the rate of events. Use of a pre-vaccination control window will deal with these issues. In a sensitivity analyses, we will use a pre-vaccination control window and a post-vaccination control window will be used for the main analysis. In a sensitivity analysis, vaccination to other non-COVID-19 vaccines will also be an exclusion and censoring event.

We will also compare the Ad26.COV2.S vaccine with active comparators with 1) only 1-dose strategy and 2) a 2-dose strategy.

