8.2.4.2. SCRI Design

For analyses of outcomes assessed with the SCRI design, the following criteria must be met. Note that the study population for each outcome-specific analysis will thus be different.

- Received a dose of Ad26.COV2.S vaccine during the study period.
- Have experienced the corresponding AESI during the control or risk window (as defined in [Table 1](#))
- Have at least one day of follow-up in both the control and the risk window.
- Have at least 12 months of data/registration in the data sources prior to start of pre-vaccination control window.

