Abbreviations: ADEM = Acute disseminated encephalomyelitis, AESI = adverse event of special interest, All non-acute events are considered to have a washout period of 365 days. * For diabetes mellitus which is a chronic condition we will use any time prior for washout.

Exacerbation of asthma ascertainment will require the definition of an asthma cohort and identifying exacerbations of asthma within that cohort.

The asthma cohort will be defined by having:

- a code for asthma and;
- at least 2 prescriptions for an inhaled corticosteroid within 5 years before the index date.

Among this asthma cohort, an exacerbation of asthma was defined by having:

- At least 1 prescription of a systemic glucocorticosteroid during the defined risk window or;

- At least 1 hospitalisation for asthma during the defined risk window.

The date of this event will be the date of the first prescription of a systemic glucocorticosteroid or the admission date for hospitalisation for asthma, whichever comes first.

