8.7.6. Sensitivity Analyses

Sensitivity analyses will be performed to:

- Assess the risk of AESI within extended disease-specific risk windows for events for which the risk interval is not well known or documented in the vaccine safety literature.
- Assess the impact of data sources that are shown not to capture vaccinations well during the feasibility assessment. In the sensitivity analyses with non-exposed comparators those data sources from the cohort analysis for the acute and non-acute events will be excluded, to avoid misclassification of exposure.
- Excluding and censoring upon the administration of other (non-COVID-19) vaccinations in the SCRI and cohort study (see Section 8.1.2.2).
- Comparing Ad26.COV2.S with active comparators with (1) a 1-dose strategy and (2) a 2-dose strategy in the cohort study.
- Conduct a SCRI analysis using a pre-vaccination control window for all acute AESIs.

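### Fixing the asthma cohort's inhaled-corticosteroid criterion at vaccination lets a control-window exacerbation lead to eligibility in the pre-vaccination SCRI when a risk-window one cannot, which pulls that rate ratio down

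*Protocol*

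**What the plan says.** Protocol section 8.3.3 builds the asthma outcome in two steps.

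- **Cohort membership** needs "a code for asthma and" "at least 2 prescriptions for an inhaled corticosteroid within 5 years before the index date". The time limit is attached to the ICS criterion; the asthma code has no date of its own.
- **The event** within that cohort is a systemic steroid prescription ("At least 1 prescription of a systemic glucocorticosteroid during the defined risk window or") or an asthma admission. The wording covers the risk window only; no control-window version is written.

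Section 8.1.2 equates the index date with vaccination: "At least one year of enrolment prior to the index date (date of vaccination) will be required".

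The endpoint in section 7 is "The incidence of asthma exacerbation within 1-14 days", listed as an acute event and therefore analysed by SCRI. On window length, section 8.1.2.1 says: "The control window will have the same maximum length as the risk window". Section 8.2.4.2 admits people who "Have experienced the corresponding AESI during the control or risk window".

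The main SCRI uses a post-vaccination control window. Section 8.7.6 adds a sensitivity analysis: "Conduct a SCRI analysis using a pre-vaccination control window for all acute AESIs". Table 5 also lists the pre-vaccination window for the stratified SCRI analyses.

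**The concern.** A self-controlled design removes fixed differences between people, but only if a case's inclusion does not depend on which window its event fell in. Here it can. The ICS look-back ends at vaccination, so it takes in the pre-vaccination control window and any gap after it, and stops before the risk window. ICS started or resumed because of a control-window exacerbation counts towards the two required prescriptions. ICS prescribed because of a risk-window exacerbation comes too late to count.

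What is at stake is the value of the check. Section 8.1.2.1 warns that a post-vaccination control window can bias towards the null when one event is captured again, and it relies on the pre-vaccination window to deal with this. Asthma exacerbations can recur. If vaccination truly raised the risk, both analyses could then err in the same direction, and their agreement would reassure without good reason.

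**Working it through.** **1. Order of events on the time axis.** In the pre-vaccination SCRI the sequence is: control window (up to 14 days), gap (length left to the SAP), vaccination, risk window (days 1–14). The ICS look-back covers the five years ending at vaccination.

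| | Exacerbation in control window | Exacerbation in risk window |
|---|---|---|
| Two or more earlier ICS prescriptions | counted | counted |
| One earlier ICS prescription, one more issued after the attack | counted if issued before vaccination | not counted |
| No earlier ICS prescription, two issued after the attack | counted if both issued before vaccination | not counted |

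Only the last two rows differ between windows, and they differ in one direction. In the main SCRI both windows follow vaccination, so neither can feed the look-back.

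**2. Size of the bias.** Let E be the control events among people who qualify independently of the attack, and X the extra control events from the last two rows. Risk events are IRR × E, and counted control events are E + X. With f = X / (E + X):

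observed IRR = IRR × E / (E + X) = IRR × (1 − f)

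The documents give nothing from which f could be derived, so it is an assumption shown as a range.

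| f (assumed) | true IRR 1 reads | true IRR 2 reads |
|---|---|---|
| 2% | 0.98 | 1.96 |
| 3% | 0.97 | 1.94 |
| 5% | 0.95 | 1.90 |
| 10% | 0.90 | 1.80 |
| 15% | 0.85 | 1.70 |
| 20% | 0.80 | 1.60 |
| 30% | 0.70 | 1.40 |

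**3. Effect on the plan's own power benchmark.** Table 4 gives 80.5% power for a relative risk of 2 with 69 cases and equal windows. It is reproduced by the signed-root likelihood-ratio formula, with two-sided α of 0.05 assumed:

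- p = RR / (1 + RR)
- A = 2[p ln RR − ln((1 + RR)/2)]
- B = (ln RR)² p(1 − p) / A
- power = Φ((√(nA) − 1.96) / √B)

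For RR = 2 and n = 69: p = 0.667, A = 0.1133, B = 0.943, √(nA) = 2.796, so power = Φ(0.861) = 80.5%.

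With n held at 69 and the biased ratio put in, power for a true relative risk of 2 is about 78% at f = 2%, 74% at 5%, 67% at 10%, 49% at 20% and 28% at 30%. This illustrates scale only; the protocol gives no expected number of asthma cases.

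**4. Check of direction.** A simulation used a true ratio of 1 and 4 million people per scenario. All its settings were assumed: a 1% event probability per window; negative binomial counts of earlier ICS prescriptions with mean 2, 6 or 15 and dispersion parameter 0.7; and a 10% to 90% chance that an attack prompts one ICS prescription, always issued before vaccination when the attack is in the control window.

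- With the criterion applied at vaccination, the ratio ran from 0.70 (few earlier prescriptions, 90% chance) to about 1 (many earlier prescriptions, 10% chance). The one value above 1, at 1.01, is simulation noise.
- With the criterion applied at the start of the control window, it lay between 0.98 and 1.02 throughout.

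**5. Washout.** The abstract's description of SCRI follow-up puts the AESI-specific washout before the pre-vaccination control window. Table 1 puts it before the index date, at 365 days for asthma exacerbation, and section 8.2.5 excludes anyone with the AESI in the washout. Taken literally, the latter pair removes every pre-vaccination control case, and the analysis cannot be run. The calculation above uses the abstract's placement.

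**The case against.** The strongest reply is that the route is narrow. The records that define an exacerbation, systemic steroids or an admission, are not ICS prescriptions. A reader might infer that the attack itself confers eligibility; the definitions do not support that. The person must be short of two ICS prescriptions over five years, must reach two after the attack, and must do so before vaccination, within at most a 14-day window plus the gap. Established ICS users qualify anyway and contribute no bias. This stands, and it is why the effect may be negligible.

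A reader might also extend the asymmetry to the asthma code. That would follow only if the code, too, must precede the index date, which the protocol does not say. The certain asymmetry is in the ICS criterion.

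It can further be said that the SAP may settle the matter, since section 8.3.3.1 leaves refined algorithms to it. But section 8.3.3 states an anchor without qualification. Elsewhere the protocol does adapt anchors to the SCRI: section 8.2.4.2 counts enrolment back from the start of the pre-vaccination control window, and section 8.3.4 measures time-varying covariates at the start of each window. The asthma cohort was not adapted, and a programmer following the text would build in the bias.

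Finally, section 8.3.2 records the regulator's request for asthma exacerbation in the feasibility assessment. It does not record a request for this SCRI analysis.

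**Conclusion.** The point holds for the SCRI analyses with a pre-vaccination control window: the sensitivity analysis in section 8.7.6 and the stratified analyses so listed in Table 5. There, case selection depends on the window, and the expected bias is downwards.

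A reader might infer that the primary asthma result is biased. It is not affected by this mechanism, because both windows of the main SCRI follow vaccination.

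Nor is 0.97 to 0.85 an estimate. It is what an assumed f of 3% to 15% implies at a true IRR of 1. The real value could be close to 1 if most cohort members are established ICS users.

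The conclusion rests on two readings: that the washout precedes the control window, and that the exacerbation definition carries over to the control window. This is a minor but real flaw in a stated rule.

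**What to change.** For the SCRI with a pre-vaccination control window, apply both asthma-cohort criteria, the asthma code and the two ICS prescriptions, at the start of that control window. Keep the index date for the cohort design. The main SCRI does not need the change; if both SCRI analyses should use the same asthma cohort, the earlier anchor can serve both without creating an asymmetry.

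At the same time, reconcile the washout placement in Table 1 and section 8.2.5 with the abstract, and state the exacerbation definition for control windows as well as risk windows.

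The cost is one anchor date in a variable definition. The five-year look-back moves back by a few weeks, and a few newly treated people drop out of the affected analyses.

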8.3.3. Evaluation of Safety Outcomes

The sponsor has created a list of AESIs based on current knowledge of the Ad26.COV2.S vaccine. [Table 1](#) lists and explains the AESIs to be ascertained in the study with specific risk windows. Background incidence rates for most of the data sources and AESIs are available on the VAC4EU dashboard <https://vac4eu.org/covid-19-tool/>. Definitions and codes are available on Zenodo (<https://zenodo.org/communities/vac4eu/>).

Table 1: AESI-Specific Risk Windows and Washout Periods for Patient Inclusion in the Study

Body System	AESI	Disease-specific washout period before the index date	Disease-specific risk window following the index date
Nervous and central nervous system	Encephalitis, including ADEM and meningoencephalitis	365 days	1-42 days
	Guillain-Barré Syndrome	365 days	1-42 days
	Transverse myelitis	365 days	1-42 days
	Bell's palsy	365 days	1-42 days
	Multiple sclerosis, including optic neuritis	365 days	1-365 days
	Sensorineural Hearing loss	365 days	1-60 days
	Generalised convulsion	365 days (w/o epilepsy) 90 days (w/o non-epileptic seizures)	1-14 days
Immune system	Autoimmune thyroiditis	365 days	1-365 days
	Immune thrombocytopenia	365 days	1-42 days
	Type 1 diabetes mellitus	Any time prior*	1-365 days
	Acute aseptic arthritis	365 days	1-365 days
	Anaphylaxis	90 days	0-2 days
Cardiac system	Cardiac inflammatory disorders, including myocarditis and pericarditis	365 days	1-28 days
	Microangiopathy	365 days	1-28 days
	Heart failure	365 days	1-28 days
	Stress cardiomyopathy	365 days	1-28 days
	Coronary artery disease, including acute myocardial infarction	365 days	1-28 days
	Arrhythmia	365 days	1-14 days
Blood and lymphatic system disorders	Deep vein thrombosis	365 days	1-28 days
	Pulmonary embolism	365 days	1-28 days
	Disseminated intravascular coagulation	365 days	1-28 days
	Non-haemorrhagic stroke	365 days	1-28 days
	Haemorrhagic Stroke	365 days	1-28 days
	thrombocytopenia	365 days	1-28 days
	peripheral thrombosis	365 days	1-28 days
	Sinus thrombosis	365 days	1-28 days
	Thrombotic Thrombocytopenia syndrome	365 days	1-28 days
	Composite: venous thrombosis	365 days	1-28 days
	Composite: arterial thrombosis	365 days	1-28 days
Composite: strokes	365 days	1-28 days	
Renal system	Acute kidney failure	365 days	1-14 days
Hepatic system	Acute hepatic failure	365 days	1-14 days
Respiratory system	Exacerbation of asthma	365 days	1-14 days

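### Exacerbation of asthma is defined only inside the risk window, which contradicts the self-controlled design that must count it in both windows

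*Protocol*

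**What the plan says.** Section 8.3.3 first defines an asthma cohort: an asthma code and "at least 2 prescriptions for an inhaled corticosteroid within 5 years before the index date". Within that cohort, an exacerbation is either of two events:

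- "At least 1 prescription of a systemic glucocorticosteroid during the defined risk window or"
- "At least 1 hospitalisation for asthma during the defined risk window"

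On dating, the section says: "The date of this event will be the date of the first prescription of a systemic glucocorticosteroid", or the date of admission for asthma if that is earlier.

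Section 7 lists the endpoint among the acute events: "The incidence of asthma exacerbation within 1-14 days". Table 1 gives the same window and a 365-day washout. Acute events are analysed primarily by SCRI, which sets the risk window against a "post-vaccination control window (main analysis) within the same individual" and, as a sensitivity analysis, against a pre-vaccination control window (Section 8.1.2.1). Section 8.2.4.2 requires that cases "Have experienced the corresponding AESI during the control or risk window". Section 8.7.1.3 reports case counts in both windows and estimates the rate ratio by conditional Poisson regression. Section 7 also puts asthma exacerbation into a time-to-onset analysis that fixes no risk window in advance.

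**The concern.** A case definition for a self-controlled comparison has to be one that can be met in either window. Here both criteria carry the risk window inside the definition. A steroid course or an asthma admission in the control window, in the year before vaccination, or on day 100 of the time-to-onset analysis is, on the wording of Section 8.3.3, not an exacerbation.

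At stake is whether a listed primary endpoint of the safety evaluation can be estimated. If the definition is programmed as written, the comparison returns an extreme result that says nothing about the vaccine. If programmers extend it on their own initiative, different data sources may extend it differently before the results are pooled.

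A second, smaller matter is specificity. The steroid criterion does not ask why the drug was prescribed. The cohort criteria limit who can have an event, not the reason for the prescription.

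**Working it through.** **1. The provisions side by side**

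| Section | What it needs |
|---|---|
| 8.3.3, exacerbation definition | event in the risk window only |
| 8.2.4.2, SCRI inclusion | event in the control or the risk window |
| 8.7.1.3, SCRI reporting and model | case counts in both windows |
| 8.2.5 and Table 1, washout | events in the 365 days before the index date |
| 7, time-to-onset | events at any time after vaccination, no window fixed |

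The first row cannot hold together with the other four. The cohort sensitivity analysis is less affected, because comparators also have a risk window after their index date.

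**2. The protocol's own SCRI figures**

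These are not in error. I used the signed-root likelihood-ratio formula with risk share r = 0.5 and two-sided alpha 0.05 (alpha is assumed; Section 8.5.2 does not state it):

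- p = RR·r/(RR·r + 1 − r)
- A = 2[p·ln RR − ln(RR·r + 1 − r)]
- B = (ln RR)²·p(1 − p)/A
- power = Φ((√(nA) − 1.96)/√B)

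For RR 2 this gives 80.5% with 69 events (Table 4: 80.5%) and 92.6% with 100 events (Table 3: 92.6%). All 19 entries checked agree to within 0.3 percentage points. The Table 3 entries printed as 100.0% were not run.

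**3. The definition applied literally**

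Section 8.1.2.1 gives the control window the same maximum length as the risk window. With full follow-up in both, a case falls in the risk window with probability RR/(1 + RR). With n₁ of n cases in the risk window, the estimate is n₁/(n − n₁). The definition forces n₁ = n, so the denominator is 0 and there is no finite estimate.

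Against RR = 1, the exact two-sided p is 2 × 0.5ⁿ:

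| n | p |
|---|---|
| 5 | 0.0625 |
| 6 | 0.031 |
| 69 | 3.4 × 10⁻²¹ |

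From six cases on, the test rejects whatever the truth. The pre-vaccination control window behaves the same way.

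**4. The steroid criterion once the window is corrected (illustrative only)**

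Let f be the share of *control-window* events that are steroid courses unrelated to asthma and to vaccination. The protocol gives no value for f. A true RR of 2 is then observed as 2(1 − f) + f = 2 − f.

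| f (assumed) | Observed RR | Power, 69 events | Events for 80% power |
|---|---|---|---|
| 0 | 2.00 | 80.5% | 69 |
| 0.10 | 1.90 | 74% | 79 |
| 0.25 | 1.75 | 63% | 103 |
| 0.50 | 1.50 | 38% | 194 |
| 0.75 | 1.25 | 15% | 634 |

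The base of the share matters. Shares of 20% and 60% of control-window events give 1.8 and 1.4. As shares of *all* events, with equal windows, they give:

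- 20%: (0.10 + 0.80 × 2/3)/(0.10 + 0.80 × 1/3) = 1.73
- 60%: (0.30 + 0.40 × 2/3)/(0.30 + 0.40 × 1/3) = 1.31

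**The case against.** The strongest reply is that nobody would run the definition this way. Sections 8.2.4.2 and 8.7.1.3 say plainly that events count in both windows. The washout and the time-to-onset analysis presuppose events outside the risk window. Section 8.3.3.1 speaks loosely of incidence within risk windows for every AESI, without anyone concluding that no AESI has control events. A programmer who met zero control cases by construction would notice. This stands as evidence of intent, and it is why the point is a contradiction and not a prediction. A reader might infer that the SCRI for asthma will in fact have no control events; the protocol as a whole does not support that. But the other sections say only where events are counted. They do not supply a definition for use outside the risk window.

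On the steroid criterion, the reply is largely right:

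- With the window wording corrected, the washout would exclude anyone with a systemic steroid prescription in the preceding 365 days, and so most long-term users.
- COVID-19 infection in the preceding month is a listed time-varying covariate (Section 8.3.4).
- Section 8.3.3.1 provides for refined algorithms in the SAP, possible case validation, and bias analysis where the predictive value is low.

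These provisions are general and not specific to asthma, but they address this kind of misclassification. A reader might infer that the steroid criterion invalidates the endpoint. The documents do not support that: no figure for unrelated steroid use is given, and the hospital criterion is specific to asthma.

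**Conclusion.** The wording of the exacerbation definition is wrong as it stands and contradicts four other provisions of the protocol. Read literally, it yields zero control-window events, no finite rate ratio, and a rejection from six cases on (p = 0.031). That p-value assumes equal windows with full follow-up; the zero count needs no assumption. Since the endpoint is one the protocol itself defines, and Section 8.7 says major changes to primary endpoint definitions go into an amendment, the correction belongs in the protocol.

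The missing asthma indication is a real but secondary limitation. Its size is unknown, and the dilution table rests entirely on assumed shares.

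Two further inferences should be avoided. The SCRI power tables need no correction. And Section 8.3.2 ties the regulator's request for this event to the feasibility assessment, so the safety endpoint should not be described as having been added at the regulator's request.

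**What to change.** Remove the window from both criteria. Define the event, within the asthma cohort, as a systemic glucocorticosteroid prescription or a hospitalisation for asthma, dated at the first of these in the period being assessed. State that the same rule applies in the washout, the risk window, the control windows, the time-to-onset analysis and comparator follow-up.

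Add a sensitivity analysis that counts hospitalisation for asthma only. If dilution is discussed, label the figures as assumption-based and define the unrelated share as a share of control-window events. A rule linking each steroid prescription to a nearby asthma code, or dropping those near a COVID-19 or other AESI code, is not required: it could discard genuine infection-triggered exacerbations.

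The cost is a wording change and a revised algorithm, using the same prescription and admission records that the definition already needs. The hospitalisation-only version will have fewer events and therefore less precision. Under the corrected rule, the washout will also exclude cohort members with a steroid prescription in the preceding year; the number excluded should be reported.
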